8.5.2. Analysis

Table 14.1.3.9: Screening and baseline disease characteristics

Continuous parameters: descriptive statistics per treatment group (and overall).

Categorical parameters: frequency tabulation per treatment group (and overall).

No formal comparison between the treatment groups is planned.

Population: the table will show

- safety
- ITT.

Table 14.1.3.10: Screening and baseline disease characteristics: Sub-group analyses

The following sub-groups will be shown:

- By target C_{trough} at Day 15
- By target C_{trough} at Day 29
- By target C_{trough} at Day 15 and 29
- By sweat chloride (from arm with greatest volume) at baseline
- By sweat chloride (mean value from both arms) at baseline
- By %FEV1 at baseline

Population: the table will show

- safety
- ITT.

Table 14.1.3.11: Screening and baseline disease characteristics: Pooled analyses

The following sub-groups will be shown:

- By target C_{trough} at Day 15
- By target C_{trough} at Day 29
- By target C_{trough} at Day 15 and 29

Population: the table will show

- safety
- ITT.

Listing 16.2.4.2: Screening and baseline disease characteristics

Listing per treatment group and per subject of all screening and baseline disease characteristics. Genotyping will be listed as well.

Population: Safety.

8.6. MEDICAL HISTORY AND CONCURRENT DISEASES

When the end date is only partially known, the missing parts will be imputed by the last day of the month/year.

Listing 16.2.4.3: Medical history

Listing per treatment group and per subject of the medical history data findings (i.e., condition no longer present at the start of the study): original terms as well as coded terms.

Population: safety.

Listing 16.2.4.4: Concomitant diseases

Listing per treatment group and per subject of the concomitant diseases data findings (i.e., condition still present or unknown): original terms as well as coded terms.

Population: safety.

8.7. PRIOR AND CONCOMITANT THERAPIES

8.7.1. Classification of Therapies

All prior and concomitant therapies will be allocated into exactly one of the following categories:

- Prior only: the therapy ended before the first study drug administration.
- Concomitant only: the therapy started on or after the first study drug administration.
- Post-treatment: the therapy started after the last study drug administration.
- Prior and concomitant: the therapy started before the first study drug administration, and ended on or after the first study drug administration.

When the start date is missing, the therapy is assumed to have started on the same day as the first administration of study drug.

When the end date is missing, the therapy is assumed to be still ongoing after the end of the study.

When the start date is only partially known, the missing parts will be imputed by the first day of the month/year, or the day of the first medication intake in case the nonmissing part matches.

When the end date is only partially known, the missing parts will be imputed by the last day of the month/year.

Imputation of start and end dates is only done for the classification into prior / concomitant / prior+concomitant. The listing will present the original start and end dates, also when incomplete. Fields like start and stop days will not be derived from imputed incomplete dates.

No further classification into analysis periods will be done.

The relative study day of therapy start and stop will be derived as follows (only listed):

Start day

= (Therapy start date) – (date of first study medication administration) + 1, when the start date of therapy is known and complete, and when the therapy start date is on or after the date of first study medication;

= (Therapy start date) – (date of first study medication administration), when the start date of therapy is known and complete, and when the therapy start date is before the date of first study medication;

= missing when the start date of therapy is unknown, missing, or incomplete.

Stop day

- = (Therapy stop date) – (date of first study medication administration) + 1, when the end date of therapy is known and complete, and the end date of therapy is on or after the date of first study medication;
- = (Therapy stop date) – (date of first study medication administration), when the end date of therapy is known and complete, and the end date of therapy is before the date of first study medication;
- = (Study termination date) – (date of first study medication administration) + 1, when the therapy is still ongoing when the subject leaves the study; in such cases the stop day will be presented as “>XX days” in the listing;
- = missing when the end date of therapy is unknown, missing or incomplete and the therapy isn’t ongoing after the subject left the study.

8.7.2. Coding of Therapies

All therapies are coded using WHO-DRUG (version 01March2017). In the table(s), the generic term will be used. The ATC classification will not be used for analysis. Multiple records of the same generic term for the same subject with the same categorization will be counted only once. The table will therefore present subjects, not occurrences.

8.7.3. Analysis

Table 14.1.3.12: Prior and concomitant therapies: Tabulation

Frequency tabulation per treatment group (and overall) of the generic terms.

Population: safety.

Listing 16.2.4.5: Prior and concomitant therapies

Listing per treatment group and per subject of all data on prior and concomitant therapies. Flags for prior/concomitant will be added. In case the therapy was due to an AE or medical history, the AE preferred term and the original term from medical history page will be mentioned in this listing.

Population: safety.

8.8. EXPOSURE TO STUDY MEDICATION AND COMPLIANCE

8.8.1. Derivations

Derived parameters for GLPG2222/Placebo intakes:

- Total treatment duration (days) = (last dose administration date – first dose administration date) + 1 day.
- Total treatment duration, excluding days off drug (days): sum of all durations (last – first +1) in the drug log pages where there is a dose >0 tablets.

- Percentage days with an intake = $100\% \times \left(\frac{\text{total treatment duration,excluding days off drug}}{\text{total duration}} \right)$
- Total compliant treatment duration (days): sum of all durations (last – first +1) in the drug log pages where there is a dose with exactly 1 tablet (for cohort A) or exactly 3 tablets (cohort B).
- Percentage compliance = $100\% \times \left(\frac{\text{total compliant treatment duration}}{\text{total duration}} \right)$

The “total duration” used as denominator in the above formulae equals: (date of Day 29 visit or early termination visit) – (date of first drug intake) + 1.

8.8.2. Analysis

Table 14.1.4.1: Exposure to study drug: Descriptive statistics

Descriptive statistics of the treatment duration (days) and the compliance (%) by treatment group.

Population: safety.

Listing 16.2.5.1: Exposure to study drug: eCRF data

Listing per treatment group and per subject of all eCRF data related to the use of drug.

Population: safety.

Listing 16.2.5.2: Exposure to study drug: Derived data

Listing per treatment group and per subject of all derived data related to the use of drug.

Population: safety.

Listing 16.2.5.3: Study drug administration (clinic visit)

Listing per treatment group and per subject of all data related to the study drug administration (morning dose at clinic and previous day).

Population: safety.

8.9. COMMENTS

Listing 16.2.5.4: Comments

Listing per treatment group and per subject of remarks and comments written in the CRF. Comments that are already presented in other parts of the analysis (e.g., lab, ECG, exposure...) do not need to be repeated in this Comments listing.

Population: safety.

9. DEFINITIONS OF EFFICACY TABLES, LISTINGS AND FIGURES

9.1. SWEAT CHLORIDE

9.1.1. Parameters

Two sweat collections, one from each arm, will be obtained from each subject at each time-point indicated in the flow chart. Sweat samples will be immediately frozen and sent to the central laboratory for testing and interpretation of results.

For the analysis, the following step should be applied for each time-point:

- Select the chloride value obtained from the collection with the greater volume of sweat (variable LBORRES when LBTESTCD = 'VOLUME' and LBSPEC = 'SWEAT' in SDTM.LB dataset). And if for a specific visit, the volume of sweat is equal for both arms then the value with the highest chloride concentration will be used.
- Select only sweat collections that have been performed pre-dose

In tables, figures and listings, this parameter will be called: Sweat Chloride (from arm with greatest volume).

A first sensitivity analysis will be done by using another method for the derivation of the sweat chloride. At each time-point, the sweat chloride value used for the analysis will be derived:

- by taking the mean of the 2 sweat collection samples (right arm and left arm respectively) if the difference between the samples is not exceeding 25 mmol/L. If the difference between the 2 samples exceeds 25 mmol/L, the results will be discarded.
- by taking the available sweat chloride value if 1) only 1 arm was measured or 2) if sufficient volume for 1 arm only was collected.

In tables, figures and listings, this parameter will be called: Sweat Chloride (mean value from both arms).

Analysis will present:

- Actual values
- Categories of actual values:
 < 40 mmol/L
 [40,50[mmol/L
 [50,60[mmol/L
 ≥ 60 mmol/L
- Change from baseline (Day 1 pre-dose):
 change at time point t = (time point t value) – (baseline value)
- Percent change from baseline (Day 1 pre-dose):
 %change at time point t = 100 x (time point t value – baseline value) / (baseline value)

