7.1. DETERMINATION OF SAMPLE SIZE

The sample size calculation is based on the expected change from baseline in sweat chloride concentration after 29 days of treatment. The standard deviation of the sweat chloride concentration change is expected to be 10 mmol/L. With an 80% power, the study will be able to detect a difference between study drug doses of 14 mmol/L at a 5% 2-sided type-I error, assuming 50 subjects are included in the study in both Cohorts A and B. In case the study is only performed in Cohort A, it will be able to detect a difference between study drug doses of 16 mmol/L with 80% power. No adjustment for multiple testing (GLPG2222 doses versus placebo) has been done on the sample size calculation as this is an exploratory study.

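### When the two arms give equal sweat volumes, SAP 9.1.1 takes the higher chloride reading; the mean of the two would avoid selecting on the outcome

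*SAP*

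**What the plan says.** Protocol 6.3.1 requires two sweat collections per time point, one from each arm, and does not say how to combine them. SAP 9.1.1 does, for every time point including baseline:

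- **Main parameter.** "Select the chloride value obtained from the collection with the greater volume of sweat". If, for a visit, "the volume of sweat is equal for both arms then the value with the highest chloride concentration will be used".
- **First sensitivity parameter.** A value derived "by taking the mean of the 2 sweat collection samples". A single arm is used if only one is usable, and the visit is discarded if the arms differ by more than 25 mmol/L.

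Both parameters go through the sweat chloride outputs of SAP 9.1.2 and 9.1.3. These include the ANCOVA, Kruskal-Wallis and Wilcoxon p-values (Table 14.2.1.1.4) and the MMRM (Table 14.2.1.1.11). Neither document gives a reason for preferring the higher reading at a tie.

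**The concern.** Choosing the arm with more sweat can be defended as a quality criterion. At equal volume that defence is gone, and the rule chooses by the value of the outcome itself. The larger of two readings is never below their mean and usually above it.

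The rule works visit by visit, so its effect need not cancel within a subject. A tie at baseline only produces an apparent fall in sweat chloride, which is the direction of benefit. A tie at a later visit only produces an apparent rise.

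The level matters too. The main parameter is cut at 40, 50 and 60 mmol/L for the frequency and shift tables (Tables 14.2.1.1.9 and 14.2.1.1.10) and for the baseline sub-groups (SAP 3.4), and at 40 and 60 for the listing flags (SAP 9.1.4). Sweat chloride is a secondary endpoint, but the sample size is built on its change.

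**Working it through.** **Inputs from the documents.** Protocol 7.1 gives the planning SD: "The standard deviation of the sweat chloride concentration change is expected to be 10 mmol/L". From it the protocol derives a detectable difference of 14 mmol/L for 50 subjects over the two cohorts (power 80%, two-sided alpha 0.05), and of 16 mmol/L if only Cohort A is run. Allocation is 2:2:1 within each cohort of 25 (Protocol 5.1), so there are 10 per dose and 5 + 5 = 10 pooled placebo.

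**Inputs assumed.** w is the SD of one arm's reading about the subject's value at that visit, with normal and independent errors and the same w in both arms; 3 to 6 mmol/L is used. The tie rate is taken as 5% to 20% of visits. If the planning SD of 10 describes a single-arm change, its variance contains 2w², so w cannot exceed √(100/2) = 7.07.

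**1. The plan's own figure.** A two-sample t-test with SD 10 and difference 14 has power 79.6% at 9 per group and 84.1% at 10 per group. Ten is therefore the smallest group size reaching 80%, and 5 × 10 = 50. The exact detectable difference at 10 versus 10 is 13.25 mmol/L, consistent with 14 as a rounded-up figure. For 10 versus 5 and a difference of 16, power is 79.7% with error degrees of freedom pooled over the three Cohort A groups (detectable difference 16.06), or 77.0% with a plain two-group test. The planning basis is reproduced closely enough.

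**2. Bias at a tied visit.** Let D be the difference between arms. The higher reading equals the mean plus |D|/2. With D ~ N(0, 2w²), E|D| = 2w/√π, so the expected excess is w/√π = 0.564w:

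| w (mmol/L) | Excess at a tied visit (mmol/L) |
|---|---|
| 3 | 1.7 |
| 5 | 2.8 |
| 6 | 3.4 |

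At the ceiling of 7.07 it is 4.0.

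**3. Variability at a tied visit.** The variance of the higher reading is w²(1 − 1/π) = 0.68w², against 0.50w² for the mean. Adding the squared bias, w²/π, gives the higher reading a mean squared error of w², the same as one arm picked at random. The mean of the two halves that, to w²/2.

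**4. Effect on a group's average level.** Tie rate × w/√π: 0.05 × 1.69 = 0.08 up to 0.20 × 3.39 = 0.68 mmol/L. For a group of 10, one subject tied at only one of the two visits moves the mean change by 0.17 to 0.34 mmol/L in expectation.

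**5. Effect on the dose-placebo contrast.** The bias is the between-group difference in tie rate × w/√π. With equal rates, simulation (w = 3, 5, 7; ties 5% to 20%) gave a bias within 0.02 mmol/L of zero. With the later-visit tie rate doubled in one group it gave 0.09 to 0.76 mmol/L.

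**6. Two-arm mean as the main value throughout.** If the SD of 10 is for a single-arm change, averaging both arms at both visits removes w² from the variance:

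| w | SD of change | Detectable difference, 10 v 10 | Power at 14 mmol/L |
|---|---|---|---|
| one arm (plan) | 10 | 13.25 | 84.1% |
| 3 | √91 = 9.54 | 12.64 | 87.3% |
| 5 | √75 = 8.66 | 11.47 | 92.7% |
| 6 | √64 = 8.00 | 10.60 | 95.9% |

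**The case against.** The tie rule is pre-specified, mechanical and identical in every group, in a blinded trial with central laboratory measurement. Inference is each dose against pooled placebo, and step 5 shows no bias there when tie rates are equal. Nothing in the documents suggests they are not. This stands, and it limits the point to individual changes, level-based outputs and avoidable noise at tied visits.

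A reader might go further and infer that the plan throws away the second collection. It does not. The two-arm mean is pre-specified and receives the same ANCOVA, non-parametric and MMRM analyses. The second reading is absent only from the main parameter.

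A reader might also infer from step 6 that the two-arm mean ought to be the main parameter. That is not established, for four reasons.

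- The gain depends on an assumed w. At w = 3 it is only 0.6 mmol/L. At w = 6, reading error would make up 72 of the total variance of 100.
- Protocol 7.1 does not say that the SD of 10 is for a single-arm change.
- The gain assumes equal precision in both arms, which a greater-volume rule implicitly denies. The mean has variance (w₁² + w₂²)/4, which exceeds w₁² once w₂ > √3·w₁ = 1.73w₁.
- The two-arm parameter discards visits with arms more than 25 mmol/L apart. Under normal errors that is about 0.04% of visits at w = 5 and 0.3% at w = 6, but gross collection errors need not be normal. LOCF then fills the gap with an earlier value, possibly baseline (SAP 5.4.2).

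None of this defends the higher reading at a tie. Where volumes are equal, volume gives no ground for thinking one arm more precise.

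**Conclusion.** The concern holds for the tie rule and is minor. At a tied visit the rule raises the value by w/√π, which is 1.7 to 3.4 mmol/L for an assumed w of 3 to 6, and doubles the mean squared error relative to averaging. It can distort an individual's change and shift a subject across a cut-off. How many subjects this touches cannot be said, because the documents give neither the tie rate nor the expected spread of baseline values.

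The documents do not support reading this as a bias in the treatment comparison. That would need tie rates that differ between groups, and even a doubling in one group gives less than 1 mmol/L, against a planned detectable difference of 14. Nor do they show that the single-arm main parameter is wrong when volumes differ.

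**What to change.** In SAP 9.1.1, replace the tie rule for the main parameter: when the two volumes are equal, use the mean of the two chloride values. State that the 25 mmol/L discard rule stays with the sensitivity parameter, so that no visit is lost from the main one. This is one sentence and a small programming change before database lock, with no new data and no conflict with the protocol.

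Optionally, make the two-arm mean the main parameter and the greatest-volume value the sensitivity analysis. Both are already defined, so this is a swap of labels, but it brings in the discard rule and the equal-precision assumption. The tie change does not depend on it.

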9.1.2. Tables

Table 14.2.1.1.1: Sweat Chloride (mmol/L): Descriptive statistics of the actual values per time point

Descriptive statistics of actual values per treatment group and analysis visit for both parameters.

Parameters:

- Sweat Chloride (from arm with greatest volume)
- Sweat Chloride (mean value from both arms)

The table will show:

- LOCF in ITT.
- OC in ITT.

Table 14.2.1.1.2: Sweat Chloride (mmol/L): Sub-group analyses: Descriptive statistics of the actual values per time point

Descriptive statistics of the actual values per treatment group and analysis visit for each sub-group.

Parameters:

- Sweat Chloride (from arm with greatest volume)
- Sweat Chloride (mean value from both arms)

The following sub-groups will be shown:

- By target C_{trough} at Day 15
- By target C_{trough} at Day 29
- By target C_{trough} at Day 15 and 29
- By sweat chloride (from arm with greatest volume) at baseline [This sub-group will be applied only for the parameter Sweat Chloride (from arm with greatest volume)]
- By sweat chloride (mean value from both arms) at baseline [This sub-group will be applied only for the parameter Sweat Chloride (mean value from both arms)]
- By %FEV1 at baseline

The table will show:

- LOCF in ITT.
- OC in ITT

Table 14.2.1.1.3: Sweat Chloride (mmol/L): Pooled analyses: Descriptive statistics of the actual values per time point

Descriptive statistics of the actual values on pooled treatment group and analysis visit.

Parameters:

- Sweat Chloride (from arm with greatest volume)
- Sweat Chloride (mean value from both arms)

The following sub-groups will be also provided in this pooled analysis:

- By target C_{trough} at Day 15
- By target C_{trough} at Day 29
- By target C_{trough} at Day 15 and 29

The table will show:

- LOCF in ITT.
- OC in ITT

Table 14.2.1.1.4: Sweat Chloride (mmol/L): Descriptive statistics of the changes from baseline per time point

Descriptive statistics of changes from baseline per treatment group and analysis visit. The actual value at baseline will also be presented in this table.

P-values are generated from an ANCOVA model on the changes from baseline at each time point with treatment as factors and baseline value as covariate. Pairwise comparison (dose group vs pooled placebo) will be provided as well.

P-values will be generated also from a Kruskal-Wallis test (overall treatment effect) and Wilcoxon rank sum test (pairwise comparison with placebo) as sensitivity analysis.

Parameters:

- Sweat Chloride (from arm with greatest volume)
- Sweat Chloride (mean value from both arms)

The table will show:

- LOCF in ITT.
- OC in ITT (only descriptive, no inferential statistics)

Table 14.2.1.1.5: Sweat Chloride (mmol/L): Descriptive statistics of the changes from baseline per time point on Placebo groups

Descriptive statistics of changes from baseline per cohort, analysis visit on placebo (cohort A), on placebo (cohort B), on pooled placebo. The actual value at baseline will also be presented in this table.

Parameters:

- Sweat Chloride (from arm with greatest volume)
- Sweat Chloride (mean value from both arms)

The table will show:

- LOCF in ITT.
- OC in ITT

Table 14.2.1.1.6: Sweat Chloride (mmol/L): Sub-group analyses: Descriptive statistics of the changes from baseline per time point

Descriptive statistics of changes from baseline per treatment group and analysis visit for each sub-group. The actual value at baseline will also be presented in this table.

Parameters:

- Sweat Chloride (from arm with greatest volume)
- Sweat Chloride (mean value from both arms)

The following sub-groups will be shown:

- By target C_{trough} at Day 15
- By target C_{trough} at Day 29
- By target C_{trough} at Day 15 and 29
- By sweat chloride (from arm with greatest volume) at baseline [This sub-group will be applied only for the parameter Sweat Chloride (from arm with greatest volume)]
- By sweat chloride (mean value from both arms) at baseline [This sub-group will be applied only for the parameter Sweat Chloride (mean value from both arms)]
- By %FEV1 at baseline

The table will show:

- LOCF in ITT.
- OC in ITT

Table 14.2.1.1.7: Sweat Chloride (mmol/L): Pooled analyses: Descriptive statistics of the changes from baseline per time point

Descriptive statistics of changes from baseline on pooled treatment group and analysis visit. The actual value at baseline will also be presented in this table.

Parameters:

- Sweat Chloride (from arm with greatest volume)
- Sweat Chloride (mean value from both arms)

The following sub-groups will be also provided in this pooled analysis:

- By target C_{trough} at Day 15
- By target C_{trough} at Day 29
- By target C_{trough} at Day 15 and 29

The table will show:

- LOCF in ITT.
- OC in ITT

Table 14.2.1.1.8: Sweat Chloride (mmol/L): Descriptive statistics of the percent changes from baseline per time point

Descriptive statistics of percent changes from baseline per treatment group and analysis visit. The actual value at baseline will also be presented in this table.

Parameters:

- Sweat Chloride (from arm with greatest volume)
- Sweat Chloride (mean value from both arms)

The table will show:

- LOCF in ITT.
- OC in ITT

Table 14.2.1.1.9: Sweat Chloride (mmol/L): Frequency tabulation per time point

Frequency table per dose group and per time point, showing the sweat chloride concentration in the following categories: < 40 mmol/L, [40,50[mmol/L, [50,60[mmol/L, \geq 60 mmol/L.

Parameters:

- Sweat Chloride (from arm with greatest volume)
- Sweat Chloride (mean value from both arms)

The table will show:

- LOCF in ITT.
- OC in ITT

Table 14.2.1.1.10: Sweat Chloride (mmol/L): Shift table versus baseline per time point

Shift table per dose group and time point versus baseline.

Parameters:

- Sweat Chloride (from arm with greatest volume)
- Sweat Chloride (mean value from both arms)

The table will show:

- LOCF in ITT.
- OC in ITT

Table 14.2.1.1.11: Sweat Chloride (mmol/L): Sensitivity analyses on the changes from baseline values

Additional sensitivity analysis will be explored by using Mixed Effects Model for Repeated Measures (MMRM). The model will include treatment and analysis visit as fixed effects and baseline as a covariate, treatment*analysis visit as interaction terms and subject as random effect. Pairwise comparisons will be presented.

Parameters:

- Sweat Chloride (from arm with greatest volume)
- Sweat Chloride (mean value from both arms)

The table will show:

- OC in ITT.

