5. INVESTIGATIONAL PLAN

5.1. OVERALL STUDY DESIGN

This is a Phase IIa, multi-center, randomized, double-blind, placebo-controlled, parallel-group study to evaluate 4 different doses of GLPG2222 administered orally and q.d. for 29 days to adult male and female subjects with a confirmed diagnosis of CF and homozygous for the F508del CFTR mutation. Eligible subjects must be on a stable concomitant medication regimen for at least 4 weeks prior to the first study drug administration and agree to continue the same regimen for the duration of the study.

A schedule of the study design is provided in Figure 3.

[figure not shown]

Figure 3: Study design

The study will consist of a screening period of maximum 4 weeks (starting when the subject has signed the informed consent form [ICF]), a treatment period of 4 weeks, and a follow-up period of 2 weeks. Enrolled subjects will come to the clinical study center at screening, on Day 1 (baseline), Day 15, Day 29, and at the follow-up visit (2 weeks after the last study drug administration).

Approximately 50 evaluable subjects are planned to be included sequentially in the study: the first 25 subjects will be assigned to Cohort A (i.e. subjects 1 to 25) and the next 25 subjects will be assigned to Cohort B (i.e. subjects 26 to 50). Subjects participating in Cohort A are not allowed to participate in Cohort B. In each study cohort, subjects will be randomized in a 2:2:1 ratio to receive:

- Cohort A: 50 mg GLPG2222, 100 mg GLPG2222 or placebo q.d. for 29 days.
- Cohort B: 200 mg GLPG2222, 400 mg GLPG2222 or placebo q.d. for 29 days.

Assessments for efficacy and safety will be performed during the study at the time points specified in the flow chart in Section 1.

Additionally, subjects can choose to participate in the optional substudy, in which nasal brushings will be collected (Section 6.7).

Subjects will be in the study for a duration of minimum 6 weeks and maximum 10 weeks (from screening until the follow-up visit, depending on the duration of the screening period).

The end of the study is defined as the last contact with the last subject.

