7.1.3. Analyses of Efficacy Parameters

Descriptive statistics of actual values, changes from baseline (pre-dose on Day 1), and percent changes from baseline will be provided.

An analysis of covariance (ANCOVA) model on the changes from baseline at each time point, with treatment as factor and baseline value as covariate, will be applied to the following parameters:

- Sweat chloride concentration;
- FEV₁;
- CFQ-R scores.

Between-group comparisons will be done for each GLPG2222 group versus the pooled placebo group (if the study is performed in both Cohorts A and B) or versus placebo in Cohort A (if the study is only performed in Cohort A).

Missing data will be imputed, also for subjects who prematurely discontinue the study. The primary imputation method will be the last-observation-carried-forward. An observed-case analysis will also be performed.

A sensitivity analysis will be performed by using non-parametric tests. The GLPG2222 groups and pooled placebo group (if the study is performed in both Cohorts A and B) or the GLPG2222 groups and placebo in Cohort A (if the study is only performed in Cohort A) will be compared using a Kruskal-Wallis test (overall treatment effect) and Wilcoxon rank sum tests (pairwise comparisons versus the corresponding placebo group).

Additional exploratory analyses and graphical presentations have been described in this SAP to better understand the data.

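### The rank-based sensitivity tests omit the baseline covariate that the ANCOVA uses; a baseline-adjusted rank test should be added beside them

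*SAP*

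**What the plan says.** Protocol 7.3.3 and SAP 7.1.3 fit an ANCOVA to the change from baseline at each time point, with treatment as factor and baseline as covariate, for sweat chloride, FEV1 and the CFQ-R scores. SAP 7.1.3 then adds: "A sensitivity analysis will be performed by using non-parametric tests". SAP 9.1.2 (Table 14.2.1.1.4) makes this concrete as a Kruskal-Wallis test for the overall effect and a "Wilcoxon rank sum test (pairwise comparison with placebo) as sensitivity analysis". No covariate, stratification or adjusted-rank version is mentioned. The same wording is used for spirometry (Table 14.2.1.2.4), CFQ-R (Table 14.2.1.3.4) and biomarkers (Table 14.2.3.4).

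Two neighbouring provisions matter. In these tables the p-values are produced on the LOCF data only, and the observed-case version is descriptive. The separate MMRM (Tables 14.2.1.1.11, 14.2.1.2.9, 14.2.1.3.9 and 14.2.3.9) keeps the baseline covariate but uses observed cases.

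Neither document says what the rank tests are meant to check, or how a disagreement with the ANCOVA will be read.

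**The concern.** The tables analyse change, so baseline is subtracted, but it is not adjusted for. Measurement error alone makes change correlate negatively with baseline, and with about 10 subjects per arm chance baseline differences are to be expected. The ANCOVA removes the part of the variation that baseline explains; the rank tests leave it in.

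A useful sensitivity analysis changes one assumption and holds the rest. Here adjustment and scale both change. The pairwise Wilcoxon also ranks only two arms, whereas the ANCOVA estimates its error from all five. No planned analysis keeps both the LOCF data and the covariate while relaxing only the distributional assumption, because the MMRM is observed-case and normal-theory. Protocol 2.6.2 says that the results will aid dose selection. A supportive p-value that misses 5% only because a covariate was dropped could blur that reading.

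**Working it through.** **Inputs.** SD of change 10 mmol/L ("The standard deviation of the sweat chloride concentration change is expected to be 10 mmol/L"); two-sided 5% ("at a 5% 2-sided type-I error"); 50 subjects over two cohorts, 25 each; allocation 2:2:1 (Protocol 5.1). Each dose arm has 25 x 2/5 = 10 subjects and each cohort 25 x 1/5 = 5 on placebo, so pooled placebo is 10. The baseline-change correlation rho is **assumed**, from 0 to -0.7.

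**The plan's own figure.** Protocol 7.1 states: "With an 80% power, the study will be able to detect a difference between study drug doses of 14 mmol/L". For 10 against 10, the normal approximation gives (1.960 + 0.842) x 10 x sqrt(1/10 + 1/10) = 12.5. A t-test gives 13.2 (18 df) or 12.8 (45 df). Power at 14 is 88%, 84% and 87%, so 14 is conservative and does not reproduce on these bases. An unadjusted Wilcoxon with 10 per arm does give 80% at 14. For Cohort A alone (10 against 5) the plan gives 16: a t-test with 22 df has 79.7% power there, but the Wilcoxon only 70%. No single method tested yields both figures. This is a separate matter and does not affect what follows.

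**Why the covariate matters.** Adjustment reduces the SD of change to 10 x sqrt(1 - rho^2), that is 10.0, 9.5, 8.7 and 7.1 at rho = 0, -0.3, -0.5 and -0.7. Dividing 14 by SD x sqrt(2/10) gives 3.13, 3.28, 3.61 and 4.38 standard errors. Without adjustment it stays at 3.13.

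**Simulation.** Five arms of 10, one dose arm shifted by 14 mmol/L, 6,000 trials per setting (Monte Carlo standard error about 0.5 points near 80%). Quade's test here ranks change and baseline within the two arms compared, regresses ranks on ranks, and compares the residuals. Power (%), normal errors:

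| rho | ANCOVA | Two-arm t, no covariate | Planned Wilcoxon | Quade, two arms | Rank ANCOVA, five arms |
|---|---|---|---|---|---|
| 0 | 85.4 | 84.0 | 80.3 | 79.8 | 82.0 |
| -0.3 | 88.8 | 84.4 | 80.3 | 82.3 | 85.2 |
| -0.5 | 93.9 | 84.1 | 79.8 | 88.5 | 90.4 |
| -0.7 | 98.8 | 84.7 | 80.0 | 95.4 | 97.1 |

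*Cost of omitting the covariate* (Quade minus Wilcoxon, both two-arm rank tests): -0.5, 2.0, 8.7 and 15.4 points. A second simulation gave 82/89/97% adjusted against 79/79/80% unadjusted at -0.3/-0.5/-0.7, that is 3, 10 and 17 points. Wilcoxon on regression residuals gained 87.5 - 79.9 = 7.6 points at -0.5, but only 81.0 - 79.9 = 1.1 at -0.33.

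*The rest of the gap* comes from ranks and from using two arms. At rho = -0.5 the total gap is 93.9 - 79.8 = 14.1 points. The covariate accounts for 8.7 and the other two for 5.4.

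Power (%), heavy-tailed errors (t, 3 df):

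| rho | ANCOVA | Planned Wilcoxon | Quade, two arms | Rank ANCOVA, five arms |
|---|---|---|---|---|
| 0 | 87.8 | 93.0 | 92.4 | 93.9 |
| -0.3 | 90.4 | 92.4 | 93.5 | 95.4 |
| -0.5 | 94.0 | 89.7 | 94.8 | 97.1 |
| -0.7 | 97.4 | 85.9 | 97.3 | 99.0 |

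Trials in which the rank test and the ANCOVA fall on opposite sides of 5% (normal data, 14 mmol/L):

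| rho | Wilcoxon | Quade | Rank ANCOVA |
|---|---|---|---|
| 0 | 9.1% | 9.8% | 6.4% |
| -0.3 | 11.0% | 9.0% | 5.5% |
| -0.5 | 15.8% | 7.5% | 5.2% |
| -0.7 | 19.2% | 3.8% | 2.2% |

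With no effect (4,000 trials per setting), the two adjusted rank tests rejected in 4.6-6.0% of trials and the Wilcoxon in 4.0-5.2%.

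**The case against.** The case against acting is substantial, and most of it stands.

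- **Use of the rank tests.** A reader might infer that the sponsor means to treat disagreement as a sign of non-normality. The documents call the tests a sensitivity analysis and say no more. The gap is that no reading is specified.
- **Power.** A reader might infer that the unadjusted Wilcoxon is systematically weaker than the ANCOVA. It is not: with heavy tails and rho of 0 or -0.3 it has more power (93.0 against 87.8%; 92.4 against 90.4%).
- **Unknown correlation.** Neither document gives a baseline SD or a baseline-change correlation, so the size of the loss is conditional. When heavy-tailed measurement error was simulated with baseline SD 12-15, adjusting the rank test gained only 0-1 point.
- **Cover elsewhere.** The MMRM keeps baseline, and Table 14.2.1.1.4 shows baseline values by group. This helps only in part, because the MMRM changes the missing-data handling and still assumes normality.
- **Imperfect cure.** An adjusted rank test still disagrees with the ANCOVA in about 2-10% of trials with exactly normal data.
- **Stakes.** These are secondary endpoints in a study that Protocol 7.1 calls exploratory, and no stated decision depends on a rank p-value.

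These points limit the claim and its priority. They do not remove the mismatch, or the fact that adjustment costs almost nothing.

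**Conclusion.** The point holds in limited form. The planned rank tests omit a covariate that the main model uses, so they differ from it in adjustment, in scale and, for the pairwise Wilcoxon, in the pooled error variance. With normal data, 10 per arm and a 14 mmol/L difference, omitting the covariate costs the rank test about 0, 2-3, 8-10 and 15-17 points of power at rho = 0, -0.3, -0.5 and -0.7. These correlations are assumptions. At -0.3 or stronger, an adjusted rank test matched or beat the planned Wilcoxon with normal and with heavy-tailed errors.

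Two further inferences are not supported. The unadjusted tests are not invalid: their type I error was at or slightly below 5%. Nor can one conclude from the 14 mmol/L figure that the trial was sized on the Wilcoxon, because the Cohort A figure of 16 does not fit that basis. Severity is low.

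**What to change.** In Tables 14.2.1.1.4, 14.2.1.2.4 and 14.2.1.3.4, and in 14.2.3.4, add a baseline-adjusted rank analysis on the LOCF data. Two options are reasonable: Quade's rank analysis of covariance, or Kruskal-Wallis and Wilcoxon tests on residuals from the regression of change on baseline. They are not the same method. The second keeps an ordinary linear fit that outliers can influence, so the SAP should name one in advance. Keep the unadjusted tests beside it, since Protocol 7.3.3 names them for the three efficacy parameters.

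Add a sentence stating that the rank analyses are supportive and that a disagreement with the ANCOVA will not be read as a test of normality, because adjustment reduces such disagreement without removing it.

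The cost is a few lines of SAP text and programming, one more set of supportive p-values, and about 1 point of power in the adjusted test if baseline and change are uncorrelated. Protocol 7.3.3 allows additional exploratory analyses, so an amendment should not be needed provided the named tests remain. The change belongs in the SAP before database lock.
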